7.2.2.2 Vital signs

Vital signs include body temperature, blood pressure, pulse, and pulse oximetry measurements. Blood pressure (systolic and diastolic) and pulse should be measured after the patient has been sitting for five minutes.

Initial Version date: 10/16/2018

Revision date: 03/11/2019, 5/07/2019, 09/26/2019, 03/17/2020, 08/26/2024

7.2.2.3 Height and weight

Height in centimeters (cm) and body weight (to the nearest 0.1 kilogram [kg] in indoor clothing, but without shoes) will be measured. Height will be measured at screening only.

7.2.2.4 Performance status

ECOG performance status will be assessed as per the assessment schedule (refer to Table 13). Assessment of ECOG performance status will be performed within the time windows described above of the scheduled assessment, even if study treatment is being held. More frequent examinations may be performed at the investigator's discretion, if medically indicated. (See [Appendix 1](#)). ECOG should be completed by a physician, nurse or other appropriately licensed personnel as delegated by the Investigator.

7.2.2.5 Laboratory evaluations

The time windows granted for laboratory evaluations are identical to the corresponding visit time windows for each visit (refer to [Section 7.1](#)).

Table 14 Clinical laboratory parameters collection plan

Test Name	Test Category
Hematology	Hgb, platelets, white blood cells (WBC), red blood cells (RBC), differential (basophils, eosinophils, lymphocytes, monocytes, neutrophils [% or absolute])
Blood Chemistry	Albumin, ALT, AST, calcium, corrected calcium, creatinine, total bilirubin, direct bilirubin (only if total bilirubin is \geq grade 2), blood urea nitrogen (BUN) or urea, potassium, sodium, fasting glucose, alkaline phosphatase, magnesium, phosphorus
Lipid Panel	HDL, LDL, triglycerides, cholesterol
Urinalysis	Macroscopic panel (dipstick) (bilirubin, blood, glucose, ketones, WBC, pH, protein, specific gravity) Reflexive Microscopic panel (RBC, WBC, casts)
Pregnancy test	At screening visit, serum pregnancy test At subsequent cycles, urinary pregnancy test.
Coagulation	International normalized ration (INR) and pro-thrombin time (PT) or Quick Test; activated partial thromboplastin time (PTT)

7.2.2.5.1 Hematology

Hematology assessments of the parameters listed in [Table 15](#) will be tested as per the schedule of assessments (Table 13).

7.2.2.5.2 Clinical chemistry

Blood chemistry assessments of the parameters listed in [Table 15](#) will be tested as per the schedule of assessments (Table 13).

7.2.2.5.3 **Coagulation**

International normalized ration (INR), prothrombin time (PT) and active partial thromboplastin time (aPPT) or Quick Test will be measured per the schedule of assessments (Table 13).

7.2.2.5.4 **Urinalysis**

Dipstick measurements will be performed as per [Table 15](#) and according to the schedule of assessments ([Table 13](#)). Any significant findings on dipstick will be followed up with microscopic evaluation as per [Table 15](#).

7.2.2.5.5 **Pregnancy and assessments of fertility**

During screening, a serum pregnancy test will be completed as per routine preoperative neurosurgical protocol prior to starting study treatment.

Women who are determined to be of child bearing potential before the study will only be tested at screening. When non-child bearing potential status is determined during the study, pregnancy testing will not be completed. Women are considered post-menopausal if they have had 12 months of natural (spontaneous) amenorrhea with an appropriate clinical profile (e.g. age appropriate, history of vasomotor symptoms), and otherwise not of child bearing potential if they have had surgical bilateral oophorectomy (with or without hysterectomy) or tubal ligation at least six weeks ago. In the case of oophorectomy alone, only when the reproductive status of the woman has been confirmed by follow up hormone level assessment is she considered not of child bearing potential.

If a positive pregnancy test is performed in between study visits, the patients must immediately notify the investigator.

8 Safety monitoring and reporting

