7.1 Protocol flow and visit schedule

[Table 13](#) lists all of the assessments and indicates when they are performed. Each post-surgical Phase 2 treatment cycle in patients is 28 days (the 28 days cycle length is fixed regardless of whether the dose of ribociclib+everolimus is withheld). All visits are to be scheduled according to the appropriate number of calendar days from Cycle 1 Day 1 of ribociclib+everolimus drug administration post-surgery. A visit window of ± 1 in Cycle 1 Days 8, 15, 22 and ± 3 days in Cycle 2 onward is allowed. PK sampling on Day 4/5 post-dose will have ± 5 min window for 0.5hr and 1 hour samples and ± 15 min window for remaining samples (2, 4, 7h).

Note: If treatment with ribociclib+everolimus is withheld at any time during the post-surgical phase (Phase 2), all study visits, and safety assessments should continue according to the appropriate number of calendar days from Cycle 1 Day 1 as per the schedule of assessments.

Surveillance imaging will adhere to current clinical standards, which include MR imaging at a minimum of every 3 months for Grade III/IV recurrent gliomas.

Table 13 Visit evaluation schedule

	PHASE 0						PHASE 2				Survival Follow Up Call/Letter
	Screening/ Baseline	Enrollment	At Home	Pre-surgical assess-ment	Craniotomy for resection tumor resection	Phase 0	Cycle 1	Cycle 2	Subsequent cycles	End of study treat-ment (EoT)	
Visit Number	1	2	n/a	3	4	5	6-9	10-13	14, 15,...	Last	
Day of cycle	-28 to-1	Day 1	Day 2 & 3	Day 4	Cohort 1&2 Day 5 or Cohort 3 Day 6	Post-Operative Visit	Day of Cycle	Day of Cycle	Day of Cycle	Last	30 days after last dose
Obtain Informed Consent	X										~every 3 months after safety phone call
Collect archival tissue	X										
Patient history											
Inclusion/exclusion criteria	X	Day 1 pre									
Diagnosis and extent of cancer	X										
Demography	X										
Relevant medical history/current medical conditions	X										
Prior antineoplastic therapy (meds, surgery, radiation)	X										
Prior/concomitant medications	X					Continuous				X	
Surgical and Medical Procedures	X	X		X	X	Continuous					
Phone Call / Letter											~Q3 months ¹³
Safety assessments											
MRI of brain	X ¹					X (post-op)	MR imaging minimum every 3 months			last MRI obtained	
Response Assessment (RANO)	X ¹					X (post-op)	minimum every 3 months			X	
Physical examination	X ²					X	1	1	1	X	
Performance status (ECOG)	X	X				X	1	1	1	X	
Height	X ²										
Weight	X ²					X	1	1	1	X	

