ECG (12-Lead)	X ²	X ^{2,4}		X ⁴	X ⁴	X	15 ⁵	1,15 ⁵	1 ^{5,6}	X	

Initial Version date: 10/16/2018

Revision date: 03/11/2019, 5/07/2019, 09/26/2019, 03/17/2020, 08/26/2024

	PHASE 0						PHASE 2					Survival Follow Up Call/Letter
	Screening/ Baseline	Enrollment	At Home	Pre- surgical assess- ment	Craniotomy for resection tumor resection	Phase 0 Follow - Up	Cycle 1 (28d)	Cycle 2 (28d)	Subsequent cycles (28d)	End of study treat- ment (EoT)	Safety Follow- up (phone)	
Visit Number	1	2	n/a	3	4	5	6-9	10-13	14, 15,...	Last		
Day of cycle	-28 to-1	Day 1	Day 2 & 3	Day 4	Cohort 1&2 Day 5 or Cohort 3 Day 6	Post- Operative Visit	Day of Cycle	Day of Cycle	Day of Cycle	Last	30 days after last dose	~every 3 months after safety phone call
Vital signs	X ²					X	1, 15	1, 15	1	X		
Adverse events			Continuous		first study drug administration up to 30 days after last dose of study treatment					X		
Laboratory assessments												
Hematology (CBC w/Diff)		X		X ⁷		X	15	1, 15	1	X		
Chemistry (CMP, Mg+, Phos)		X ²		X ⁷		X	15	1, 15	1	X		
eGFR ³		X ²		X ⁷								
Coagulation (PT/INR, PTT)		X ²		X ⁷								
Lipid panel		X ²								1 ⁸		
Urinalysis (dipstick) with microscopic analysis		X ²					15	1	1			
Pregnancy test (serum HCG) if applicable		X ²										
Pregnancy test (urine) if applicable						X	1	1	1	X		
Study Drug												
Drug administration		X ⁹	X ⁹	X ⁹	X ⁹		Daily Days 1-28 day cycle ¹⁰					
Review of Home Dosing Diary and Symptom Diary				X			1	1	1	X		
PK & Biomarker sample collections												
PK Blood Sampling		X		X ¹¹	X ¹¹		1, 8, 15, 22 10	1, 8, 15, 22 10				
Collection of PK CSF					X							
Collection of PK/PD Tumor tissue					X					X ¹²		
Biomarker blood collection		X ²										

1 | The most recent MRI scan available should be utilized.

	PHASE 0						PHASE 2					Survival Follow Up Call/Letter
	Screening/ Baseline	Enrollment	At Home	Pre-surgical assessment	Craniotomy for resection tumor resection	Phase 0	Cycle 1	Cycle 2	Subsequent cycles	End of study treatment (EoT)	Safety Follow-up (phone)	
Visit Number	1	2	n/a	3	4	5	6-9	10-13	14, 15,...	Last		
Day of cycle	-28 to-1	Day 1	Day 2 & 3	Day 4	Cohort 1&2 Day 5 or Cohort 3 Day 6	Post-Operative Visit	Day of Cycle	Day of Cycle	Day of Cycle	Last	30 days after last dose	~every 3 months after safety phone call

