7.1.1.11.1 Day 1 Enrollment

The following assessments will be performed on Day 1:

- Review of surgical and medical procedures
- ECOG
- 12-lead ECG
- Collection of AEs and Concomitant medication(s)
- Screening assessments not previously collected as noted in section [7.1.1.9](#)
- Day 1 pre-dose PK sample
- Day 1 pre-dose biomarker blood sample
- Confirm eligibility prior to study drug administration
- In clinic/hospital study drug administration
- Provide the patient the following for home dosing on Days 2 and 3
 - Instructions for study medication
 - Dosing Diary
 - Symptom Diary
 - Study drug

7.1.1.11.2 Day 2 and 3

Phase 0 patients will record study drug administration in the Dosing Diary and record symptoms in the Symptom Diary.

7.1.1.11.3 Day 4

The following assessments will be performed on Day 4:

- Review of medical and surgical procedures
- Collection of AEs and Concomitant medication(s)
- Review of home dosing diary and symptom diary

- 12-lead ECG
- Trough PK Sample (Dose Levels 0-3)
- Laboratory testing (may also be performed as a pre-surgical assessment on Day 5 or Day 6):
 - Chemistry, (comprehensive metabolic panel, magnesium, phosphorus)
 - Hematology (CBC w/differential)
 - Coagulation (PT/INR, aPTT)
 - eGFR
- In clinic/hospital study drug administration
- PK blood sampling: 0.5, 1, 2, 4, 7 hours post-dose (Dose Levels 0-3)
 - *In Dose Level 4+ only, PK blood sampling will occur on Day 5 instead of Day 4.*

7.1.1.11.4 **Day 5**

- Review of medical and surgical procedures
- Collection of AEs and Concomitant medication(s)
- 12-Lead ECG (if not collected on Day 4)
- In clinic/hospital study drug administration
- Craniotomy (Day 5 for Cohort 1 & 2; Day 6 for Cohort 3)
 - PK Collection of blood, CSF and tumor
 - Biomarker tumor collection
- Dose Level 1-3: Day 5 trough/24hrs post-dose
- Dose Level 4+ only: PK blood sampling: pre, 0.5, 1, 2, 4, 6, 8 and 24 hours (Day 6) post-dose

7.1.1.11.5 **Follow-up / EOT visit**

Phase 0 patients will have a follow up visit 7-14 days after surgery (routine post-operative visit). All Phase 2 patients should be scheduled for an EOT visit within 7 (± 3) days following discontinuation of study treatment.

The following assessments will be performed at the EOT visit:

- Physical exam
- ECOG performance status
- Weight
- Vital signs
- Laboratory blood collections
 - CMP, magnesium, phosphorus
 - Hematology (CBC w/differential)
 - Urine pregnancy test (if applicable)
- 12-lead ECG

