The required sample size will be from 6 (when Level 0 becomes MTD) to 32 patients (if dose Levels 1-5 are expanded to 6 and the time cohort is expanded to 8 additional patients). The expected sample size for the Phase 2 dose expansion study will be at most 3 to 12 patients under the assumption that at most 50% of Phase 0 dose escalation patients will have PK/PD responses. Considering the drop-out rate of 20%, the total required sample size will be approximately 30 patients.

Table 15 Target Accrual

Phase 0 Study	Cohort 1 Target Accrual	Cohort 2 Target Accrual	Cohort 3 Target Accrual
High-grade Glioma	3-11	3-20	3-11

The Phase 2 dose expansion study will be considered an exploratory study and no formal statistical comparison will be carried out. Thus, in this case, its outcome will be summarized with descriptive statistics (N, median, mean, standard deviation, minimum, maximum, and the 80% confidence interval [CI] for the mean).

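### Section 7.2.2.5.5 limits pregnancy testing of women of child-bearing potential to screening, while Table 13, Table 14 and the EOT visit list schedule later urine tests for them

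*Combined protocol and SAP*

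**What the plan says.** Section 7.2.2.5.5 (Pregnancy and assessments of fertility) first requires a serum pregnancy test during screening, before treatment starts. It then says: "Women who are determined to be of child bearing potential before the study will only be tested at screening". The next sentence reads: "When non-child bearing potential status is determined during the study, pregnancy testing will not be completed".

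The scheduling parts of the protocol say something different:

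- Section 7.1 introduces Table 13 as the table that "lists all of the assessments and indicates when they are performed".
- Table 13 has two pregnancy rows. The serum row, "Pregnancy test (serum HCG) if applicable", is a screening assessment that footnote 2 allows on Day 1 before dosing. The urine row, "Pregnancy test (urine) if applicable", is marked at the Phase 0 post-operative visit, on Day 1 of Cycle 1, Cycle 2 and subsequent cycles, and at end of treatment.
- Table 14 (clinical laboratory parameters) gives the serum test at screening and then: "At subsequent cycles, urinary pregnancy test".
- The EOT assessments in section 7.1.1.11.5 include "Urine pregnancy test (if applicable").

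**The concern.** The sentence in 7.2.2.5.5 and the three schedules give opposite instructions for the same women. The sentence is an operative rule about who is tested and when.

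Pregnancy has direct consequences in this protocol. It requires withdrawal (7.1.1.13 and 8.4) and a report within 24 hours (8.4). Phase 2 treatment continues until progression or unacceptable toxicity (4.1.2), so a single test at screening cannot detect a pregnancy that begins cycles later. Without the urine tests, detection depends on the patient having a test on her own initiative and reporting it.

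What is at stake is participant safety and consistent conduct across up to three sites. No estimate, error rate or sample size is involved.

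**Working it through.** The plan states no figure on this point, so the check is a comparison of texts followed by a count of scheduled tests.

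**1. Pregnancy tests for a woman of child-bearing potential, by source**

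| Source | At or before first dose | After first dose |
|---|---|---|
| 7.2.2.5.5, disputed sentence | Yes | None |
| Table 13 | Serum | Urine: post-operative visit, Day 1 of each Phase 2 cycle, end of treatment |
| Table 14 | Serum | Urine at subsequent cycles |
| 7.1.1.11.5 EOT list | Not covered | Urine at EOT |

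Table 14 and the EOT list each contradict the sentence on their own, so the conflict does not depend on how the columns of Table 13 are read.

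**2. Can the texts be reconciled?**

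- *Through the qualifier "if applicable".* No. A urine pregnancy test is relevant to women who could become pregnant, and that is the group the sentence restricts to screening. The following sentence takes out women found not to be of child-bearing potential. Read literally, the two sentences leave essentially nobody for the urine row.
- *By confining the sentence to the five-day Phase 0.* No. It carries no such limit, and Table 13 marks a urine test in the Phase 0 follow-up column.
- *From within 7.2.2.5.5.* The following sentence ends testing once non-child-bearing status is established during the study. That makes sense only if testing during the study was intended.

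**3. Tests lost per woman**

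For k Phase 2 cycles, Table 13 schedules after screening:

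1 (post-operative) + k (Day 1 of each cycle) + 1 (end of treatment) = k + 2

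| Cycles k | Table 13 | Disputed sentence |
|---|---|---|
| 1 | 1 + 1 + 1 = 3 | 0 |
| 2 | 1 + 2 + 1 = 4 | 0 |
| 6 | 1 + 6 + 1 = 8 | 0 |

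A Phase 0 woman who does not continue to Phase 2 would lose one test, the post-operative one.

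**4. Number of women affected**

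Section 9.7.1 states: "The expected sample size for the Phase 2 dose expansion study will be at most 3 to 12 patients". The documents do not give the share who are women of child-bearing potential. As an assumption, take a share s of 5% to 25%. The expected number is N × s:

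- N = 3: 3 × 0.05 = 0.15 to 3 × 0.25 = 0.75
- N = 12: 12 × 0.05 = 0.6 to 12 × 0.25 = 3.0

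**The case against.** The strongest opposing case accepts the conflict and disputes its weight.

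- **Other safeguards and likely practice.** Table 13 is declared to be the full list of assessments and three sources agree with one another, so most sites would follow them. A negative serum test is needed before treatment (inclusion 10), highly effective contraception is required during dosing and for three months after (exclusion 29), and a positive test between visits must be notified at once (7.2.2.5.5). This stands. It limits the practical risk and is why the point is not rated as critical. It does not make the sentence correct.
- **The urine row is not strictly empty.** A woman whose status is unresolved at entry, for example after oophorectomy alone while hormone results are awaited, falls under neither sentence. That is true, but the reading is strained and the group very small. It cannot be what rows covering every cycle were written for.
- **Inclusion 10 is wider than child-bearing potential.** It requires a negative serum test unless the patient has had a hysterectomy, so a post-menopausal woman with a uterus is also tested at screening. Replacement wording must not narrow this. Keeping the opening sentence of 7.2.2.5.5, and saying that women not of child-bearing potential are not tested *further*, avoids the problem.
- **The head count rests on an assumed share.** It does. It shows only that the numbers are small, and the finding does not depend on it.

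**Conclusion.** The concern holds. The sentence in 7.2.2.5.5 contradicts Table 13, Table 14 and the EOT list, and no reasonable reading brings them together. Followed as written, it removes all k + 2 scheduled post-screening tests for the women they are meant for.

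The tables are very likely the intended rule. They agree with one another, section 7.1 gives Table 13 the governing role, and contraception is required throughout dosing. A missing *not* before the reference to child-bearing potential would explain the sentence, but that is an inference the documents do not confirm. The contradiction stands without it.

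The scale is small: an expected 0.15 to 3 women in Phase 2, if 5% to 25% of its 3 to 12 patients are of child-bearing potential, plus one lost test for each such woman who stops after Phase 0. This should be corrected as a drafting inconsistency in a safety rule. It is not evidence of a decision to stop monitoring, and it leaves the endpoints, DLT rules and sample size untouched.

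**What to change.** Change 7.2.2.5.5 to match the tables, and leave the tables as they are. Keep the section's opening sentence on the screening serum test, so that inclusion 10 continues to decide who has it. Replace the disputed sentence with:

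> Women of child-bearing potential will have a serum pregnancy test at screening and urine pregnancy tests per Table 13 (post-operative visit, Day 1 of each Phase 2 cycle, EoT); women determined not to be of child-bearing potential will not be tested further.

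Inserting the apparently missing *not* would also remove the contradiction, but naming the Table 13 visits leaves no room for a second reading.

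The cost is one sentence in an amendment. No visit, sample or procedure is added, because every test is already in Table 13.

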8.1 Adverse events

8.1.1 Definitions and reporting

An adverse event is defined as the appearance of (or worsening of any pre-existing) undesirable sign(s), symptom(s), or medical condition(s) that occur after patient's signed informed consent has been obtained. Adverse Events that are not serious will be captured following first administration of study drug.

Abnormal laboratory values or test results occurring after study drug administration are adverse events only if they induce clinical signs or symptoms, are considered clinically significant, require therapy (e.g., hematologic abnormality that requires transfusion or hematological stem cell support), or require changes in study medication(s).

Information about all AEs is collected.

Except for screening failures, adverse events that begin or worsen after the first study drug administration should be recorded. Conditions that were already present at the time of informed consent should be recorded as part of medical history. Adverse event monitoring should be

continued for at least 30 days following the last dose of ribociclib+everolimus treatment. Adverse events (including lab abnormalities that constitute AEs) should be described using a diagnosis whenever possible, rather than individual underlying signs and symptoms. When a clear diagnosis cannot be identified, each sign or symptom should be reported as a separate Adverse Event.

Adverse events will be assessed according to the Common Terminology Criteria for Adverse Events (CTCAE) version 4.03.

If CTCAE grading does not exist for an adverse event, the severity of mild, moderate, severe, and life-threatening, corresponding to Grades 1 - 4, will be used. CTCAE Grade 5 (death) will not be used in this study; rather, information about deaths will be collected through the study.

The occurrence of adverse events should be sought by non-directive questioning of the patient (subject) during the screening process after signing informed consent at each visit during the study. Adverse events also may be detected when they are volunteered by the patient (subject) during the screening process or between visits, or through physical examination, laboratory test, or other assessments. As far as possible, each adverse event should be evaluated to determine:

1. The severity grade (CTCAE Grade 1-4)
2. Its duration (Start and Ongoing at End of study)
3. Its relationship to the ribociclib and/or everolimus treatment (Reasonable possibility that AE is related: No, Yes)
4. Action taken with respect to study or investigational treatment (none, dose adjusted, temporarily interrupted, permanently discontinued, unknown, not applicable)
5. Whether medication or therapy was given (no concomitant medication/non-drug therapy, concomitant medication/non-drug therapy)
6. Whether it is serious, where a serious adverse event (SAE) is defined as in [Section 8.2.1](#)

All adverse events should be treated appropriately. If a concomitant medication or non-drug therapy is given, this action should be recorded.

Once an adverse event is detected, it should be followed until its resolution or until it is judged to be permanent, and assessment should be made at each visit (or more frequently, if necessary) of any changes in severity, the suspected relationship to the ribociclib+everolimus treatment, the interventions required to treat it, and the outcome.

Progression of malignancy (including fatal outcomes), if documented, should not be reported as a serious adverse event.

Events that are clearly consistent with the expected pattern of progression of the underlying disease should not be recorded as AEs. Events that are clearly related to surgical complications experienced as a result of the craniotomy and not related to study participation or the test article(s) should not be recorded as AEs. If there is any indication that the event may be related to study participation or the test article, the event should be recorded as an adverse event.

Adverse events separate from the progression of malignancy (example, deep vein thrombosis at the time of progression or hemoptysis concurrent with finding of disease progression) will be reported as per usual guidelines used for such events with proper attribution regarding relatedness to the drug.

